4.2 Trial Treatments

The treatment to be used in this trial is outlined below in Table 2

Drug	Dose/Potency	Dose Frequency	Route of Administration	Regimen/Treatment Period	Use
Pembrolizumab	200 mg	Q3W	IV infusion	Day 1 of each 3 week cycle, up to 35 cycles	Experimental
Rituximab	375 mg/m ²	QW	IV infusion	Cycle 1 Day 1,8, 15; and Cycle 2 Day 1	Approved dosing regimen
Obintuzumab	1000 mg (flat dose)	QW x 4 doses, then Q3 months up to total 6 additional doses as extended therapy	IV infusion	Cycle 1 Day 1,8, 15; and Cycle 2 Day 1. If at least SD or better, proceed to extended therapy: day 1 of cycle 5, 9,13,17,21,25 if tolerated/nonprogressing	Approved dose, with attenuation of interval and total cumulative dose

Table 2	Trial	Treatment
---------	-------	-----------

4.2.1 Dose Selection/Modification

4.2.1.1 Dose Selection

The rationale for selection of doses to be used in this trial is provided in Section 3.0 - Background and Rationale.

Details on preparation and administration of pembrolizumab are provided in the Pharmacy Manual.

4.2.1.2 Dose Modification (Escalation/Titration/Other)

Adverse events (both non-serious and serious) associated with pembrolizumab exposure may represent an immunologic etiology. These adverse events may occur shortly after the first dose or several months after the last dose of treatment. Pembrolizumab must be withheld for drug-related toxicities and severe or life-threatening AEs as per Table 3 below. See Section 5.6 for supportive care guidelines, including use of corticosteroids. Table 3 lists dose modifications for pembrolizumab. Note that dose modification of rituximab, and management of rituximab-related infusion reactions, will follow institutional standard of care and investigator/sub-investigator discretion and is not specified in this protocol.

Table 3 Dose modification and toxicity management guidelines for immune-related AEs associated with pembrolizumab

Toxicity	Hold Treatment For Grade	Timing for Restarting Treatment	Treatment Discontinuation	
Diarrhea/Colitis	Z-3 Toxicity resolves to Grade 0-1 to reduce corticosteroid t		Toxicity does not resolve within 12 weeks of last dose or inability to reduce corticosteroid to 10 mg or less of prednisone or equivalent per day within 12 weeks	
	4	Permanently discontinue	Permanently discontinue	
AST, ALT, or	2	Toxicity resolves to Grade 0-1	Toxicity does not resolve within 12 weeks of last dose	
Increased Bilirubin 3-4		Permanently discontinue (see exception below) ^a	Permanently discontinue	
Type 1 diabetes mellitus (if new onset) or Hyperglycemia	T1DM or 3-4	Hold pembrolizumab for new onset Type 1 diabetes mellitus or Grade 3-4 hyperglycemia associated with evidence of beta cell failure	Resume pembrolizumab when patients are clinically and metabolically stable	
Hypophysitis	2-4	Toxicity resolves to Grade 0-1. Therapy with pembrolizumab can be continued while endocrine replacement therapy is instituted	Toxicity does not resolve within 12 weeks of last dose or inability to reduce corticosteroid to 10 mg or less of prednisone or equivalent per day within 12 weeks	
Hyperthyroidism	3	Toxicity resolves to Grade 0-1	Toxicity does not resolve within 12 weeks of last dose or inability to reduce corticosteroid to 10 mg or less of prednisone or equivalent per day within 12 weeks	
	4	Permanently discontinue	Permanently discontinue	
Hypothyroidism		Therapy with pembrolizumab can be continued while thyroid replacement therapy is instituted	Therapy with pembrolizumab can be continued while thyroid replacement therapy is instituted	

Protocol v4.0 dated 21 July 2021

Page 19 of 62

Toxicity	Hold Treatment For Grade	Timing for Restarting Treatment	Treatment Discontinuation	
Pneumonitis	2	Toxicity resolves to Grade 0-1	Toxicity does not resolve within 12 weeks of last dose or inability to reduce corticosteroid to 10 mg or less of prednisone or equivalent per day within 12 weeks.	
Fneumonitis	Recurrent grade 2, or grade 3-4	Permanently discontinue	Permanently discontinue	
Renal Failure or Nephritis	2	Toxicity resolves to Grade 0-1	Toxicity does not resolve within 12 weeks of last dose or inability to reduce corticosteroid to 10 mg or less of prednisone or equivalent per day within 12 weeks	
_	3-4	Permanently discontinue	Permanently discontinue	
	1 or 2	Withhold	• Based on severity of AE administer corticosteroids	• Ensure adequate evaluation to confirm
Myocarditis	3 or 4	Permanently discontinue		etiology and/or exclude other causes
	Intolerable/ persistent Grade 2 ^b	Withhold	Based on severity of AE administer corticosteroids	• Ensure adequate evaluation to confirm etiology or exclude other
All Other immune- related AEs	3	Withhold or discontinue based on the event ^c .		causes
	4 or	Permanently discontinue		
	recurrent	-		
	Grade 3			
		severe or Grade 3 drug-related AE that rec gin treatment with Grade 2 AST or ALT, if AS		r equal to 50% relative to baseline

^a For patients with liver metastasis who begin treatment with Grade 2 AST or ALT, if AST or ALT increases by greater than or equal to 50% relative to baseline and lasts for at least 1 week then patients should be discontinued.\

^b Patients with intolerable or persistent Grade 2 drug-related AE may hold study medication at physician discretion. Permanently discontinue study drug for persistent Grade 2 adverse reactions for which treatment with study drug has been held, that do not recover to Grade 0-1 within 12 weeks of the last dose.
^c Events that require discontinuation include but are not limited to: Guillain-Barre Syndrome, encephalitis, Stevens-Johnson Syndrome and toxic epidermal

^c Events that require discontinuation include but are not limited to: Guillain-Barre Syndrome, encephalitis, Stevens-Johnson Syndrome and toxic epidermal necrolysis.

Dosing interruptions are permitted in the case of medical / surgical events or logistical reasons not related to study therapy (e.g., elective surgery, unrelated medical events, patient vacation, and/or holidays). Subjects should be placed back on study therapy within 3 weeks of the scheduled interruption. The reason for interruption should be documented in the subject's study record.

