4.3.3 Supportive Care Guidelines

Subjects should receive appropriate supportive care measures as deemed necessary by the treating investigator, including medications for management of rituximab-related infusion reactions which may be administered per institutional standard of care.

Suggested supportive care measures for the management of adverse events with potential immunologic etiology are outlined below. Where appropriate, these guidelines include the use of oral or intravenous treatment with corticosteroids as well as additional anti-inflammatory agents if symptoms do not improve with administration of corticosteroids. Note that several courses of steroid tapering may be necessary as symptoms may worsen when the steroid dose is decreased. For each disorder, attempts should be made to rule out other causes such as metastatic disease or bacterial or viral infection, which might require additional supportive care. The treatment guidelines are intended to be applied when the investigator determines the events to be related to pembrolizumab.

Note: if after the evaluation the event is determined not to be related, the investigator does not need to follow the treatment guidance (as outlined below). Refer to Table 4 for dose modification.

It may be necessary to perform conditional procedures such as bronchoscopy, endoscopy, or skin photography as part of evaluation of the event.

When study interventions are administered in combination, attribution of an adverse event to a single component is likely to be difficult. Therefore, while the investigator may attribute a toxicity event to pembrolizumab alone, to rituximab alone, to obinutuzumab alone, or to the combination, for adverse events listed below, all interventions must be held according to the criteria below.

When study interventions are administered in combination, if the AE is considered immunerelated, all interventions should be held according to recommended dose modifications.

Participants may not have any dose modifications (no change in dose or schedule) of pembrolizumab in this study.

- If the toxicity does not resolve or the criteria for resuming treatment are not met, the participant must be discontinued from all study interventions.

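### Section 4.2.1.2 leaves rituximab dose modification to discretion, but 4.3.3 sets hold and stop rules for it; two pointers misdirect, and Grade 2 myocarditis has two different rules

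*Combined protocol and SAP*

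**What the plan says.** Section 4.2.1.2 sets the pembrolizumab holds through Table 3 and then turns to rituximab. It reads "Note that dose modification of rituximab, and management of rituximab-related infusion reactions, will follow institutional standard of care" and continues that this is a matter for "investigator/sub-investigator discretion and is not specified in this protocol". For supportive care it tells the reader: "See Section 5.6 for supportive care guidelines, including use of corticosteroids".

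Section 4.3.3 covers toxicity under combination treatment:

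- It accepts that "while the investigator may attribute a toxicity event to pembrolizumab alone, to rituximab alone, to obinutuzumab alone, or to the combination", but then rules that "for adverse events listed below, all interventions must be held according to the criteria below".
- It adds that "if the AE is considered immunerelated, all interventions should be held according to recommended dose modifications".
- If the toxicity persists or the conditions for resuming are not satisfied, "the participant must be discontinued from all study interventions".
- If the toxicity does resolve, the investigator may restart the combination. Where the antibody or the combination was blamed, pembrolizumab may be resumed alone.

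Section 4.3.3 also sends the reader to Table 4 for dose modification. On myocarditis, Table 3 withholds pembrolizumab at Grades 1 and 2 and stops it at Grades 3 and 4. The myocarditis entry in 4.3.3 withholds at Grade 1 only and stops permanently from Grade 2 upwards.

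**The concern.** One section tells the investigator that the protocol contains no rituximab rule. Another contains a mandatory one. An investigator who relies on 4.2.1.2 could give a rituximab dose that 4.3.3 requires to be held, and the pointer in 4.2.1.2 does not lead to the place that would correct this. What is at stake is patient safety and uniform dosing across patients. The myocarditis difference raises the same kind of problem for pembrolizumab: Table 3 leaves room to give it again after a Grade 2 event, and 4.3.3 does not.

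**Working it through.** This is a comparison of texts, with two small counts.

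**1. Does dose modification include a hold?** Table 3, in the same section as the rituximab sentence, carries dose modification in its title and consists of holds, restarts and discontinuations. Section 4.3.3 speaks of drugs being held under the recommended dose modifications. So the protocol's own usage includes holding and stopping, and the two sections address the same thing.

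**2. The two rules side by side (Arms A and B).**

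| Question | 4.2.1.2 | 4.3.3 |
|---|---|---|
| Is there a protocol rule for rituximab? | No; local standard and discretion | Yes |
| Listed or immune-related event at a hold grade | Discretion | Hold all drugs, including rituximab |
| Toxicity persists, or resumption conditions unmet | Discretion | Stop all drugs |
| Rituximab infusion reaction | Local practice | Local practice |

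The conflict is in the second and third event rows only. On infusion reactions the sections agree.

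**3. The limits of the hold.** It applies at the grades set by the 4.3.3 criteria and the recommended dose modifications, not to every listed event at every grade. Under Table 3, pembrolizumab continues in hypothyroidism, and hyperthyroidism is held only from Grade 3.

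**4. Where it matters most.** From Table 2 in Section 4.2, rituximab is given on cycle 1 days 1, 8 and 15 and cycle 2 day 1. Pembrolizumab is given on day 1 of each cycle.

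- Rituximab doses: 4.
- Rituximab doses on a pembrolizumab day: 2 (cycle 1 day 1, cycle 2 day 1).
- Rituximab-only doses: 4 − 2 = 2 (cycle 1 days 8 and 15).

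Take, for illustration, Grade 2 pneumonitis found at the day 8 visit. Table 3 holds pembrolizumab, but none is due that day. Only 4.3.3 says to hold the rituximab that is due.

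**5. Patients to whom the sentence applies.** From the Trial Summary, Arms A, B and C plan up to 20, 17 and 25.

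- Arms A and B: 20 + 17 = 37.
- All arms: 20 + 17 + 25 = 62.
- Share: 37 / 62 = 0.597, about 60%.

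**6. Pointers.** Section 5.0 is the Trial Flow Chart and contains only 5.1, so Section 5.6 does not exist; the supportive care guidelines are Section 4.3.3. Table 4 deals with pembrolizumab infusion reactions. The immune-related grades are in Table 3, which 4.3.3 never cites. This has a practical effect, because the 4.3.3 entries for colitis, diabetes or hyperglycemia, hypophysitis, thyroid, hepatic and renal events describe treatment without giving hold grades.

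**7. Myocarditis (all three arms).** At Grade 2, Table 3 gives withhold and 4.3.3 gives permanent discontinuation. The row labels in the extracted Table 3 are displaced, but the reading is secure: the renal row has its own Grade 2 and Grade 3-4 entries, and the Grade 1 or 2 line pairs with the myocarditis line for Grade 3 or 4.

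**The case against.** The strongest reply is that the two sections can be obeyed together. Section 4.2.1.2 grants a general discretion, 4.3.3 is specific and mandatory and names rituximab, and holding rituximab breaches neither. Harm requires someone to act on 4.2.1.2 without 4.3.3, within a window of four doses. That stands, and it keeps the point minor. It does not make the statement in 4.2.1.2 true, and the broken pointer makes the lapse easier. It can also be said that 4.3.3 elsewhere uses dose modification to mean a change in dose or schedule of pembrolizumab; that does not displace the usage in Table 3. Table 4 does carry dose modification in its title, so the pointer to it is incomplete rather than empty, but it still omits the immune-related grades.

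Three stronger readings are tempting, and the documents do not support them.

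- A reader might infer that rituximab must be held for any listed or immune-related event. Both hold sentences are tied to criteria, and some listed events carry no hold.
- A reader might infer that Table 3 and 4.3.3 also disagree on Grade 3 neurological events. Table 3's general row says "Withhold or discontinue based on the event", and its footnote gives an open-ended list of events requiring discontinuation that includes Guillain-Barre syndrome and encephalitis. The specific neurological rule in 4.3.3 fits within that choice.
- A reader might infer that the 4.3.3 sentences on relatedness to pembrolizumab undo the hold. They refer to treatment guidance and follow text on corticosteroids and other anti-inflammatory agents. The hold is stated separately and applies whichever drug is blamed.

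**Conclusion.** The point holds, at minor severity. The rituximab sentence in 4.2.1.2 is inaccurate for Arms A and B wherever 4.3.3 and the recommended dose modifications require a hold or a stop. Both pointers misdirect. The Grade 2 myocarditis rules conflict in all three arms.

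The 37 of 62 counts patients to whom the rituximab sentence applies, not patients harmed, and it does not describe the myocarditis conflict. The number who would have a hold-level event during the rituximab doses cannot be derived from the documents. A reader might look for an effect on the primary analysis; none is shown, and ORR, sample size and decision thresholds are unaffected. The conclusion rests on reading dose modification to include holding and stopping, which is how Table 3 and 4.3.3 use it.

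**What to change.** 1. Amend 4.2.1.2 so that, where Table 3 or 4.3.3 requires a hold or discontinuation for a listed or immune-related event, rituximab is held, restarted or stopped under the same rules. Keep the 4.3.3 option to resume pembrolizumab alone. Confine the discretion sentence to rituximab infusion reactions and other non-immune rituximab toxicity not listed in 4.3.3.
2. Change Section 5.6 to Section 4.3.3. In 4.3.3, cite Table 3 for immune-related events and keep Table 4 for pembrolizumab infusion reactions.
3. Align Table 3 with 4.3.3 on Grade 2 myocarditis, that is, permanent discontinuation. Nothing in the documents says which text prevails, and choosing the stricter rule is a clinical decision, so the sponsor should confirm it.

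Optionally, state in 4.3.3 that the relatedness sentences govern supportive treatment and not the hold.

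The cost is protocol wording in 4.2.1.2, including Table 3, and in 4.3.3. No design figure changes.

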4.2.2 Timing of Dose Administration

Trial treatment should be administered on Day 1 of each cycle after all procedures/assessments have been completed as detailed on the Trial Flow Chart (Section 6.0). Trial treatment may be administered up to 3 days before or after the scheduled Day 1 of each cycle.

All trial treatments will be administered on an outpatient basis.

Pembrolizumab 200 mg will be administered first (on days when rituximab is also given) as a 30 minute IV infusion every 3 weeks. Sites should make every effort to target infusion timing to be as close to 30 minutes as possible. However, given the variability of infusion pumps from site to site, a window of -5 minutes and +10 minutes is permitted (i.e., infusion time is 30 minutes: -5 Protocol v4.0 dated 21 July 2021 Page 20 of 62

min/+10 min). Rituximab will be given as per institutional standard, after pembrolizumab when co-administered on the same day.

The Pharmacy Manual contains specific instructions for the preparation of the pembrolizumab infusion fluid and administration of infusion solution.

4.2.3 Trial Blinding/Masking

This is an open-label trial; therefore, the investigator and subject will know the treatment administered.

4.3 Concomitant Medications/Vaccinations (allowed & prohibited)

Medications or vaccinations specifically prohibited in the exclusion criteria are not allowed during the ongoing trial. If there is a clinical indication for one of these or other medications or vaccinations specifically prohibited during the trial, discontinuation from trial therapy or vaccination may be required. The investigator should discuss any questions regarding this with the Merck Clinical team. The final decision on any supportive therapy or vaccination rests with the investigator and/or the subject's primary physician.

4.3.1 Acceptable Concomitant Medications

All treatments that the investigator considers necessary for a subject's welfare may be administered at the discretion of the investigator in keeping with the community standards of medical care. All concomitant medication will be recorded including all prescription, over-the-counter (OTC), herbal supplements, and IV medications and fluids. If changes occur during the trial period, documentation of drug dosage, frequency, route, and date may also be included.

All concomitant medications received within 28 days before the first dose of trial treatment and 30 days after the last dose of trial treatment should be recorded. Concomitant medications administered after 30 days after the last dose of trial treatment should be recorded for SAEs and ECIs as defined in Section 7.2.

4.3.2 Prohibited Concomitant Medications

Subjects are prohibited from receiving the following therapies during the Screening and Treatment Phase (including retreatment for post-complete response relapse) of this trial:

- Antineoplastic systemic chemotherapy or biological therapy
- Immunotherapy not specified in this protocol
- Chemotherapy not specified in this protocol
- Investigational agents other than pembrolizumab
- Radiation therapy

- Note: Radiation therapy to a symptomatic solitary lesion or to the brain may be allowed at the investigator's discretion.
- Live vaccines within 30 days prior to the first dose of trial treatment and while participating in the trial. Examples of live vaccines include, but are not limited to, the following: measles, mumps, rubella, varicella/zoster, yellow fever, rabies, BCG, and typhoid vaccine.
- Systemic glucocorticoids for any purpose other than management of rituximab-related hypersensitivity/infusion reactions; to modulate symptoms from an event of clinical interest of suspected immunologic etiology, or as physiologic corticosteroid replacement therapy for adrenal or pituitary insufficiency.

Subjects who, in the assessment by the investigator, require the use of any of the aforementioned treatments for clinical management should be removed from the trial. Subjects may receive other medications that the investigator deems to be medically necessary.

The Exclusion Criteria describes other medications which are prohibited in this trial.

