- Myocarditis: Ensure adequate evaluation to confirm etiology or exclude other causes.
 - a. For Grade 1 events, withhold pembrolizumab.
 - b. For Grade 2-4 events, permanently discontinue pembrolizumab.
 - c. Administer corticosteroids based on severity of the AE.
- **Exfoliative Dermatologic Conditions:** Ensure adequate evaluation to confirm etiology or exclude other causes.
 - a. For **suspected** SJS (Stevens-Johnson syndrome), TEN (toxic epidermal necrolysis), or DRESS (Drug reaction with eosinophilia and systemic symptoms), withhold pembrolizumab.
 - b. For confirmed SJS, TEN, or DRESS, permanently discontinue pembrolizumab.
 - c. Administer corticosteroids based on severity of the AE.
- **Management of Infusion Reactions**: Signs and symptoms usually develop during or shortly after drug infusion and generally resolve completely within 24 hours of completion of infusion.

Table 4 below shows treatment guidelines for subjects who experience an infusion reaction associated with administration of pembrolizumab (pembrolizumab). Management of rituximab or obinutuzumab infusion reactions will be performed according to institutional practice and investigator judgment.

Table 4 Pembrolizumab Infusion Reaction Dose Modification and Treatment Guidelines

NCI CTCAE Grade	Treatment	Premedication at
		Subsequent Dosing

Grade 1 Mild reaction; infusion interruption not indicated; intervention not	Increase monitoring of vital signs as medically indicated until the participant is deemed medically stable in the opinion of the investigator.	None
indicated		
Grade 2	Stop Infusion.	Participant may be
Requires therapy or	Additional appropriate medical therapy may include	premedicated 1.5h (\pm 30
infusion interruption	but is not limited to:	minutes) prior to infusion of
but responds promptly	IV fluids	with:
to symptomatic	Antihistamines	Diphenhydramine 50 mg po
treatment (e.g.,	NSAIDs	(or equivalent dose of
antihistamines,	Acetaminophen	antihistamine).
NSAIDs, narcotics, IV	Narcotics	Acetaminophen 500-1000
fluids); prophylactic	Increase monitoring of vital signs as medically	mg po (or equivalent dose of
medications indicated	indicated until the participant is deemed medically	analgesic).
for ≤ 24 hrs	stable in the opinion of the investigator.	
	If symptoms resolve within 1 hour of stopping drug	
	infusion, the infusion may be restarted at 50% of the	
	original infusion rate (e.g. from 100 mL/hr to 50	
	mL/hr). Otherwise dosing will be held until symptoms	

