6.1.4.2 Treatment Period

The treatment period begins with the first administration of study treatment, and is designated as Cycle 1 Day 1.

- **6.1.5 Induction phase:** The induction phase will consist of four cycles lasting 3 weeks: pembrolizumab 200 mg on day 1 every 3 weeks, and rituximab (Arms A and B) or obinutuzumab (Arm C) on day 1 (after pembrolizumab) x 4 doses (Cycle 1 day 1, 8, 15, and cycle 2 day 1).
- **6.1.6 Extended Therapy Phase:** Patients with at least a partial response may continue on extended therapy: pembrolizumab 200 mg day 1 every 3 weeks for up to 2 years maximum of 35 infusions.) In addition, for arm C, patients with stable disease or better, who are experiencing clinical benefit in the judgment of the investigator, may receive up to 6 more doses of obinutuzumab every 3 months (cycles

5,9,13,17,21,and 25) in combination with pembrolizumab every 21 days, up to 35 cycles.

6.1.6.1 Discontinuation of Study Therapy after CR: Patients may elect to stop therapy during the extended therapy phase, if in CR after at least 8 cycles (24 weeks) of pembrolizumab therapy. CR may be defined by CT, PET-CT, either in conjunction with biopsy when applicable (including marrow assessment). These patients are eligible for the Second Course period as in section 6.1.6.2 if no cancer treatment was administered since the last dose of pembrolizumab, the subject meets the safety parameters listed in the Inclusion/Exclusion criteria, and the trial is open. Ninety days after receiving the last dose of pembrolizumab, subjects in CR who are potential retreatment candidates may convert to standard of care surveillance visits, while remainingeligible for the Second Course period as in 6.1.6.2.

6.1.6.2 Second Course (retreatment) Period:

Subjects who elect to stop study therapy for proven CR are eligible for up to one year of additional pembrolizumab therapy, and for Arm C patients q12 week obinutuzumab (maximum of 6 courses q 3 months, and 10 total doses, including all prior doses) if they progress after stopping study treatment.

This retreatment is termed the Second Course Phase of this study and is only available if the study remains open and the subject meets the following conditions:

• Stopped therapy after receiving at least 8 cycles (24 weeks), and attaining an investigator-determined CR (CT, PET-CT, and/or biopsy-proven CR).

AND

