6.7 Reporting of Events of Clinical Interest (ECI)

Selected non-serious and serious adverse events are also known as Events of Clinical Interest (ECI) as defined below and must be reported within 2 business days to Merck Global Safety. (Attn: Worldwide Product Safety; [contact]).

For the time period beginning when the consent form is signed until treatment allocation/randomization, any ECI, or follow up to an ECI, that occurs to any subject must be reported within 2 business days to Merck Global Safety if it causes the subject to be excluded from the trial, or is the result of a protocol-specified intervention, including but not limited to washout or discontinuation of usual therapy, diet, placebo treatment or a procedure.

For the time period beginning at treatment allocation/randomization through 90 days following cessation of treatment, or 30 days following cessation of treatment if the subject initiates new

anticancer therapy, whichever is earlier, any ECI, or follow up to an ECI, whether or not related to Merck product, must be reported within 2 business days to Merck Global Safety.

Events of clinical interest for this trial include:

1. an overdose of Merck product, as defined in Section 6.3 - Definition of an Overdose for This Protocol and Reporting of Overdose to Merck, that is not associated with clinical symptoms or abnormal laboratory results.

2. an elevated AST or ALT lab value that is greater than or equal to 3X the upper limit of normal and an elevated total bilirubin lab value that is greater than or equal to 2X the upper limit of normal and, at the same time, an alkaline phosphatase lab value that is less than 2X the upper limit of normal, as determined by way of protocol-specified laboratory testing or unscheduled laboratory testing.

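### The steroid exception in section 4.3.2 covers rituximab infusion reactions only, leaving Arm C's obinutuzumab reactions under a prohibition that carries removal from the trial

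*Combined protocol and SAP*

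**What the plan says.** Section 4.3.2 lists therapies barred during screening and treatment, including the retreatment period. One item is "Systemic glucocorticoids for any purpose other than management of rituximab-related hypersensitivity/infusion reactions". The same item allows two other uses: controlling symptoms of an event of clinical interest with a suspected immune cause, and physiologic replacement for adrenal or pituitary insufficiency. The section then says that subjects who, in the investigator's assessment, "require the use of any of the aforementioned treatments for clinical management should be removed from the trial".

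The antibody differs by arm. The induction text under section 6.1.4.2 gives "rituximab (Arms A and B) or obinutuzumab (Arm C) on day 1", and Table 2 and the flow chart in section 5.1 agree. No Arm C patient receives rituximab on study.

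Section 4.3.3, in the text introducing Table 4, treats the two antibodies alike: "Management of rituximab or obinutuzumab infusion reactions will be performed according to institutional practice and investigator judgment". Two other places name rituximab only. Section 4.2.1.2 says that "dose modification of rituximab, and management of rituximab-related infusion reactions, will follow institutional standard of care and investigator/sub-investigator discretion". The opening sentence of 4.3.3 allows supportive care, "including medications for management of rituximab-related infusion reactions which may be administered per institutional standard of care".

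**The concern.** The exception in 4.3.2 was written for the antibody used in Arms A and B. Arm C uses a different antibody, and the exception does not mention it. The prohibition has a stated consequence, so the omission is more than loose drafting: staff who treat an obinutuzumab reaction with steroids under 4.3.3 and keep the patient on study depart from the words of 4.3.2.

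At stake is the handling of individual Arm C patients, who could be taken off study for receiving ordinary treatment of a foreseeable reaction, and an avoidable question of protocol deviation when they are not. The reaction is foreseeable on the protocol's own account. Section 3.1.5 names infusion reactions as an exception to the otherwise similar safety of the two antibodies, citing grade 3-4 rates of 11% with obinutuzumab and 5% with rituximab.

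**Working it through.** The plan states no figure that depends on this wording, so the check is a comparison of the texts.

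1. **Does the infusion-reaction exception reach Arm C?** No. It is limited to rituximab-related reactions, and Table 2, the flow chart and the induction text give Arm C obinutuzumab instead.

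2. **Does another exception in 4.3.2 reach it?** Physiologic replacement does not. The exception for immunologic events of clinical interest does not name antibody infusion reactions. Section 6.7 introduces its list with "Events of clinical interest for this trial include" and gives two items, an overdose without symptoms and a liver-test pattern. Section 6.1.2.1 uses the term more broadly, for adverse events of unknown cause associated with pembrolizumab that may be immune-related. Even on that broader use, a recognised reaction to an obinutuzumab infusion is not a natural fit. On days 8 and 15 of cycle 1 the flow chart gives obinutuzumab without pembrolizumab. The authors also listed rituximab reactions separately from immunologic events, which suggests they thought infusion reactions needed their own exception.

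3. **What follows from the prohibition?** The sentence after the list in 4.3.2 says such subjects should be removed. The permission that closes the paragraph covers other medications, that is, ones not on the list.

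4. **What does 4.3.3 say?** It leaves obinutuzumab infusion reactions to institutional practice and the investigator. It does not mention steroids, so the two sections diverge only where institutional practice uses them. The protocol itself regards steroids as a treatment for infusion reactions: 4.3.2 makes an exception for them with rituximab, and Table 4 lists corticosteroids for grade 3-4 pembrolizumab reactions.

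5. **Is the difference deliberate?** Nothing in the documents gives a reason to allow steroids for one antibody's reactions and not the other's. Other text also lags behind the three-arm design: section 7.0 opens by describing two patient groups, and section 4.2.2 gives the same-day dosing order for rituximab only. An incomplete update is the likelier explanation.

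6. **Do the other rituximab-only sentences have the same effect?** No. Section 4.2.1.2 and the opening of 4.3.3 say what may be done. Neither bars anything or leads to removal, and 4.3.3 itself goes on to name obinutuzumab.

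**The case against.** The strongest reply is that the protocol already protects these patients. Section 4.3 says that "The final decision on any supportive therapy or vaccination rests with the investigator" or the subject's primary physician, and that a clinical indication for a prohibited medication may require discontinuation, not that it must. Section 4.3.1 allows treatments the investigator considers necessary. The reasons for mandatory discontinuation in section 4.5 do not name use of a prohibited medication, and 4.3.2 says should, subject to the investigator's assessment. All of this stands, and it makes actual removal unlikely. It is general discretion, however, and does not rewrite a specific prohibition that has its own removal sentence.

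Several stronger readings are tempting and are not supported:

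- A reader might infer a direct contradiction between 4.3.2 and 4.3.3. The latter is silent on steroids, so the inconsistency depends on institutional practice.
- A reader might treat the list in 6.7 as closed. Section 6.1.2.1 uses the term more widely. A closed list would also put the steroids that 4.3.3 directs for pneumonitis or colitis outside the exceptions, which cannot be intended.
- A reader might see the same defect in 4.2.1.2 and throughout 4.3.3. Those sentences are permissive.
- A reader might size the problem by applying the cited 11% to 25 patients (25 × 0.11 = 2.75). That counts grade 3-4 reactions, not steroid-treated ones, and omits lower grades. It also assumes the cited rate carries over and that Arm C fills, although section 7.2.2 says at most 25 and section 7.1.3 allows a stop after 12.

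**Conclusion.** The point holds as a wording error in an operative rule. As written, 4.3.2 allows systemic steroids for rituximab infusion reactions but not for obinutuzumab ones, and directs removal of an Arm C patient who needs them. This is inconsistent with 4.3.3 wherever institutional practice treats such reactions with steroids, which is the one assumption the conclusion needs. The omission itself is certain from the text; how often it would matter is not known.

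No magnitude is claimed, because the documents give no rate of steroid use for these reactions. No endpoint definition, sample size, error rate or stopping rule depends on the sentence. A reader might infer that removals would distort the Arm C response rate, but the documents give no basis for expecting removals in practice. Grade 3-4 pembrolizumab infusion reactions are outside the point, since Table 4 already ends study drug for those patients.

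**What to change.** In section 4.3.2, change the exception to read *rituximab- or obinutuzumab-related hypersensitivity/infusion reactions*. That edit alone removes the inconsistency.

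For consistency only, add obinutuzumab to the opening sentence of 4.3.3 and to the matching sentence of 4.2.1.2. The latter also covers dose modification, so both halves of that sentence should be considered if it is edited.

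The cost is one necessary wording change and two optional ones, with no extra patients, procedures or analyses.
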